7.1 Screening (within 4 weeks (+/- 1 week) of first TACE)

Prior to randomization, each patient will have the following performed:

- Obtain informed consent
- Medical history, including demographics and disease history
- Physical exam, including vital signs, height (baseline only) and weight
- Recording of concomitant medications
- ECG
- Urinalysis (Specific Gravity, Protein, Glucose, Blood)

- Baseline laboratory tests
 - CBC (RBC, WBC, Platelet Count, Hemoglobin, Hematocrit, ANC)
 - AST
 - ALT
 - AFP
 - Total Bilirubin
 - Albumin
 - aPTT/PT/INR
 - Alkaline phosphatase
 - Serum creatinine
 - HCG for premenopausal female patients (baseline only)
- ECOG Performance Status evaluation
- Child-Pugh stage calculation
- Cardiac ejection fraction testing. Subsequent cardiac ejection fraction testing during the protocol specified treatment period must use the same method as at screening.
- Baseline MRI (first study MRI) for tumor assessment (including chest and pelvis), reviewed by Central Reviewers
 - MRI of the liver must be done at baseline to assess hepatic tumors. For those sites at which assessment for presence of extrahepatic disease has been done by CT of the chest and pelvis as the facility standard of care, those results are acceptable in place of MRI of the chest and pelvis so that additional imaging is not performed unnecessarily.

If patient meets all the inclusion criteria and none of the exclusion criteria, the patient will be randomized to a treatment group.

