7.3 MRI and Laboratory evaluations following First TACE Cycle

MRIs of the liver, chest and pelvis and laboratory evaluations must be done within 4 weeks (± 1 week) of the first TACE cycle. If the patient received chemoembolization for bilobar disease, the MRIs and laboratory tests must be done within 4 weeks (± 1 week) of the embolization of the second lobe.

Laboratory evaluations will include those listed under screening, at a minimum, and results will be reviewed by the investigator and clinically significant changes from baseline will be reported as adverse events. Additionally, blood samples will be drawn for PK analysis. MRI results of the liver will be reviewed by Central Reviewers. If the patient has experienced a cardiac related adverse event, cardiac ejection fraction testing will be done.

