7.5 MRI and Laboratory evaluations following Second TACE Cycle

MRIs of the liver, chest and pelvis and laboratory evaluations must be done within 4 weeks (± 1 week) of the second TACE cycle. If the patient received treatment for bilobar disease, the MRIs and laboratory tests must be done within 4 weeks (± 1 week) of the embolization of the second lobe.

Laboratory evaluations will include those listed under screening, at a minimum, and results will be reviewed by the investigator and clinically significant changes from baseline will be reported as adverse events. MRI results of the liver will be reviewed by Central Reviewers. Cardiac ejection fraction testing will be done for all patients and must use the same method as at screening.

If the results of the liver MRI done after the second TACE cycle, as interpreted by the Central Reviewers, demonstrate complete necrosis according to mRECIST criteria, then the patient will not have a third TACE cycle. The patient will proceed to Post Final Study TACE evaluations defined in section 7.8.

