APPENDIX F

IMAGE ACQUISITION GUIDELINE

Document file name: Image Acquisition Guideline v 1.0

Document version: 1.0

Version date: 17-November-2009

Author:

[REDACTED]
[REDACTED]
[REDACTED]
[REDACTED]
[REDACTED]

INTRODUCTION

The following acquisition guidelines have been developed for standardization of the study imaging components across radiology centers participating in the phase 3 prospective, randomized, blinded and controlled investigation of Hepasphere/Quadrasphere microspheres for delivery of doxorubicin for the treatment of hepatocellular cancer.

Important Notes

- Regularly scheduled imaging for this study should be acquired in strict adherence to these guidelines
- Optimization of image acquisition protocols and consistency in the use of the same protocol throughout follow-up examinations are key for proper application of modified RECIST criteria
- Please ensure blinding of all confidential site/patient information on all images. Subject number should be entered in lieu of patient name
- Images sent for independent blinded review should be clear of any tumor markings or annotations determined at the site
- Imaging data, including raw/original data, shall remain archived at the site for the duration of the study
- Utilization of dynamic contrast-enhanced magnetic resonance (MR) imaging is mandatory if not medically contraindicated
- In dynamic MR studies, it is mandatory to obtain a dual-phase imaging of the liver. Every effort should be made to time the contrast administration for all studies so that high-quality arterial-phase imaging is obtained throughout the liver parenchyma on the first run, and high-quality portal venous-phase imaging is obtained throughout the liver parenchyma on the second run
- The tables below show preferred parameters. Please use parameters as close to these as possible. Once the values shown below have been selected, they should remain consistent throughout the trial for a given subject

LIVER MR IMAGING

- Scanner type: 1.5 - 3.0 Tesla
- Phased array coil
- Breath-hold or ultrafast sequences required
- T1-weighted imaging: spoiled gradient echo sequences preferred (SGE, FLASH, SPGR)
- T2-weighted imaging: turbo/fast spin echo sequences preferred (TSE, FSE)
- Interval (slice thickness plus gap) should not exceed 7mm

SCAN 1 (PRE-CONTRAST)

Patient Orientation	Supine
Scan Locations/Coverage	Dome of the right diaphragm (or higher to ensure complete coverage of the liver) through the entire liver

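### Chest and pelvis may be imaged by CT at baseline but must be imaged by MRI after every TACE cycle, so disease unseen on the baseline CT could be recorded as new extrahepatic spread

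*Combined protocol and SAP*

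**What the plan says.** Section 7.1 sets MRI as the default at screening: "Baseline MRI (first study MRI) for tumor assessment (including chest and pelvis), reviewed by Central Reviewers". It then makes an exception for sites at which "assessment for presence of extrahepatic disease has been done by CT of the chest and pelvis as the facility standard of care"; at those sites "those results are acceptable in place of MRI of the chest and pelvis so that additional imaging is not performed unnecessarily". The liver must still be imaged by MRI.

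The exception appears only under screening. After cycle 1, Section 7.3 states: "MRIs of the liver, chest and pelvis and laboratory evaluations must be done within 4 weeks (± 1 week) of the first TACE cycle". After cycle 2, Section 7.5 states: "MRIs of the liver, chest and pelvis and laboratory evaluations must be done within 4 weeks (± 1 week) of the second TACE cycle". Section 7.7 repeats the requirement for cycle 3. Footnote 6 to the Schedule of Procedures in Appendix A and Section 4.1 of the radiology charter likewise name only MRI after baseline.

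No section asks for the baseline chest and pelvis modality to be kept, or says how a CT baseline is to be compared with a later MRI. For ejection fraction, by contrast, Section 7.1 requires that later tests "must use the same method as at screening".

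**The concern.** A patient with a CT baseline who is managed exactly as written has chest and pelvis assessed by CT once and by MRI from then on. The first on-study judgement about extrahepatic spread is therefore made across two methods. If MRI shows something that was there at entry but not visible on CT, it will look like spread that arose on study.

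The plan uses such a finding in three places:

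- **TTUP**, a tertiary objective, counts extrahepatic spread as an event (Sections 2 and 11.5.6).
- **ORR-T**, a secondary objective, counts extrahepatic spread as progression in its Section 2 definition.
- **Withdrawal of Patients** lists progression to extrahepatic disease among the reasons for which the investigator may withdraw a patient.

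**Working it through.** The plan gives no figure on this point, so there is none to reproduce. The check is a comparison of the imaging rules, followed by an illustrative calculation on declared assumptions.

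**1. Modality by time point**

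| Time point | Liver | Chest and pelvis | Source |
|---|---|---|---|
| Baseline | MRI | MRI, or CT where that is site standard of care | 7.1 |
| After cycle 1 | MRI | MRI | 7.3 |
| After cycle 2 | MRI | MRI | 7.5 |
| After cycle 3 | MRI | MRI | 7.7 |

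The visit in Section 7.8 has no imaging. No modality is set for survival follow-up, when the treating physician judges untreatable progression.

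**2. Number of transitions.** A CT-baseline patient has one CT-to-MRI comparison, at the first follow-up. The second and third follow-up scans each have an earlier study MRI to compare with. So there is about one transition per patient.

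**3. Direction of the error.** Exclusion criterion (i) removes patients with extrahepatic spread, so every eligible patient starts with none found.

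- Disease present at entry, not shown on CT and shown on MRI: it is recorded as new spread. This error comes from the switch.
- New spread that follow-up MRI misses or shows late: this would happen equally after an MRI baseline. It reflects MRI sensitivity, not the switch.

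Only the first is attributable to the inconsistency.

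**4. Which outcomes it reaches**

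- Overall survival, the primary endpoint, does not depend on imaging.
- Overall ORR uses the last post-TACE liver MRI (Section 11.5.2), and the liver is imaged by MRI throughout.
- TTUP and withdrawal are exposed.
- ORR-T is exposed by its Section 2 definition. However, Section 11.5.5 confines the analysis to treated areas of the liver, and Sections 7.3, 7.5, 7.7 and 10 send the Central Reviewers only the liver MRI.

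**5. Illustrative size.** Enrolment is 255 × 2 = 510 (Section 11.2). The other two inputs are assumptions with no source in the documents: 20-50% of patients with a CT baseline, and 1-3% misclassified per CT-to-MRI transition.

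Patients affected = 510 × share with CT baseline × 1 transition × error rate

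- Low: 510 × 0.20 × 1 × 0.01 = 1.02
- High: 510 × 0.50 × 1 × 0.03 = 7.65

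That is about 1 to 8 patients. If no site used CT at baseline, the number would be zero.

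**The case against.** The strongest reply is that this is a small wording gap on lower-tier outcomes. Much of that stands. The primary endpoint and overall ORR are outside it. TTUP is tertiary, and after study treatment the treating physician judges it with no modality specified, so the proposed sentence would not standardise that period. Withdrawal is at the investigator's discretion, and nothing prevents further imaging of an equivocal finding.

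The plan's own consistency principle is also weaker support than it seems. Appendix F says optimisation and "consistency in the use of the same protocol throughout follow-up examinations are key for proper application of modified RECIST criteria", but its acquisition parameters cover liver MR only. Appendix G says extrahepatic disease is measured by conventional RECIST rather than by viable-tumour diameter. The ejection-fraction rule concerns a number compared with thresholds, not presence or absence of spread. Both show that the plan values a constant method; neither is a rule for chest and pelvis.

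Three stronger readings are tempting, and the documents do not support them:

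- *The switch hides or misdates true spread.* Patients enter with none found, and follow-up MRI would miss new spread equally after an MRI baseline.
- *Every follow-up scan is a cross-modality comparison.* Multiplying by two to three scans would give 510 × 0.20 × 2 × 0.01 = 2.04 to 510 × 0.50 × 3 × 0.03 = 22.95, or about 2 to 23. Those would be comparisons rather than patients, and only the first crosses modalities.
- *The arms are biased against each other.* CT use is a site practice, and Section 6 controls treatment balance within site. The expected effect is similar error in both arms.

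A further objection is that keeping the baseline modality leaves follow-up methods differing between sites. Within-site balance answers this: each arm should have a similar mix.

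**Conclusion.** The inconsistency between Section 7.1 and Sections 7.3, 7.5 and 7.7 is in the text and should be reconciled. Its consequence is narrow: pre-existing disease not shown on a baseline CT may be recorded as new extrahepatic spread at the first follow-up MRI. This bears on TTUP and withdrawal, and on ORR-T by definition, although the route from a chest or pelvis scan to the ORR-T analysis is doubtful as written.

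The expected effect is misclassification of similar size in both arms, which can blur a difference but is not shown to create one. The range of about 1 to 8 of 510 patients is illustrative only. The documents give no share of CT baselines, no detection rates for either method and no expected rate of extrahepatic spread, and the conclusion does not depend on that range. That a change of method can mimic new disease is a reasonable inference; the documents neither state nor quantify it. This is an inexpensive improvement, not a threat to the trial's main result.

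**What to change.** Add to Sections 7.3, 7.5 and 7.7: *At follow-up, chest and pelvis are imaged with the same modality as at that patient's baseline; the liver is always imaged by MRI.* Align footnote 6 of the Schedule of Procedures and Section 4.1 of the radiology charter.

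Record the chest and pelvis modality at each time point. Add a sensitivity analysis of TTUP and ORR-T by baseline modality. For patients already scanned, the modality should be recoverable, since Appendix F requires sites to archive imaging data for the duration of the study.

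The cost is a short amendment and one data field. CT-baseline patients would have CT radiation after each cycle and possibly a separate scan session, because the liver still needs MRI. It should not be assumed that these CTs are routine: Section 7.1 calls CT standard of care only for an extrahepatic assessment already done at baseline, and the documents do not show that repeat CT after each cycle is standard at those sites. If the sponsor judges that cost too high, the alternative is to keep MRI at follow-up, state how a CT baseline is to be compared with the first MRI, and run the same sensitivity analysis.

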7.2 First TACE Cycle

A TACE cycle is defined as a single embolization for patients with unilobar disease or an embolization of each lobe for patients with bilobar disease.

First TACE embolization must be within 4 weeks (\pm 1 week) of baseline MRI and laboratory evaluations.

If a patient has bilobar disease, the first lobe must undergo chemoembolization within 4 weeks (\pm 1 week) of baseline MRI and laboratory evaluations, and the second lobe must undergo chemoembolization within 4 weeks (\pm 1 week) of the first lobe.

A blood sample will be drawn the morning after the first embolization between 6am and 8am for PK analysis for all patients. For patients with bilobar disease, this sample is drawn after the embolization of the first lobe. An additional PK blood sample will be drawn 6-8 hours after the first sample for those patients who have not been discharged.

7.3 MRI and Laboratory evaluations following First TACE Cycle

MRIs of the liver, chest and pelvis and laboratory evaluations must be done within 4 weeks (± 1 week) of the first TACE cycle. If the patient received chemoembolization for bilobar disease, the MRIs and laboratory tests must be done within 4 weeks (± 1 week) of the embolization of the second lobe.

Laboratory evaluations will include those listed under screening, at a minimum, and results will be reviewed by the investigator and clinically significant changes from baseline will be reported as adverse events. Additionally, blood samples will be drawn for PK analysis. MRI results of the liver will be reviewed by Central Reviewers. If the patient has experienced a cardiac related adverse event, cardiac ejection fraction testing will be done.

7.4 Second TACE Cycle

A second TACE cycle is required for all patients, unless the investigator deems further treatment unsafe for the patient. The second TACE cycle must be within 8 weeks (± 2 weeks) of first TACE cycle.

If the patient has bilobar disease, the first lobe of the second TACE cycle must undergo chemoembolization within 8 weeks (± 2 weeks) of the second lobe in the first TACE cycle, and the second lobe of the second TACE cycle must undergo chemoembolization within 4 weeks (± 1 week) of first lobe in the second TACE cycle.

7.5 MRI and Laboratory evaluations following Second TACE Cycle

MRIs of the liver, chest and pelvis and laboratory evaluations must be done within 4 weeks (± 1 week) of the second TACE cycle. If the patient received treatment for bilobar disease, the MRIs and laboratory tests must be done within 4 weeks (± 1 week) of the embolization of the second lobe.

Laboratory evaluations will include those listed under screening, at a minimum, and results will be reviewed by the investigator and clinically significant changes from baseline will be reported as adverse events. MRI results of the liver will be reviewed by Central Reviewers. Cardiac ejection fraction testing will be done for all patients and must use the same method as at screening.

If the results of the liver MRI done after the second TACE cycle, as interpreted by the Central Reviewers, demonstrate complete necrosis according to mRECIST criteria, then the patient will not have a third TACE cycle. The patient will proceed to Post Final Study TACE evaluations defined in section 7.8.

7.6 Third TACE Cycle

A third TACE cycle will be done for patients with MRI results for the liver after the second TACE cycle that demonstrate less than complete necrosis, as interpreted by the Central Reviewers, according to mRECIST criteria. The third TACE cycle must be done within 8 weeks (± 2 weeks) of the second TACE cycle. If the patient has bilobar disease, the first lobe of the third TACE cycle must undergo chemoembolization within 8 weeks (± 2 weeks) of the second lobe of the second

TACE cycle, and the second lobe of the third TACE cycle must undergo chemoembolization within 4 weeks (\pm 1 week) of the first lobe in the third TACE cycle.

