This is a phase 3, multicenter, randomized, controlled study designed to evaluate the safety and effectiveness of treating patients with localized, non resectable hepatocellular carcinoma with conventional transarterial chemoembolization (cTACE) or HepaSphere/QuadraSphere transarterial chemoembolization (hqTACE).

The study will consist of a screening period in which patient eligibility will be determined. Patients meeting the study entry criteria will be randomized on a 1:1 basis to receive either cTACE or hqTACE. A TACE cycle is defined as a single embolization for patients with unilobar disease and an embolization of each lobe for patients with bilobar disease. Patients will receive up to 3 TACE cycles. The first embolization will be done within 4 weeks of baseline imaging, and the second and third TACE cycles will take place 8 and 16 weeks after the first TACE cycle, respectively. MRIs will be done 4 weeks after each TACE cycle to determine tumor response and will be assessed by Central Reviewers.

The primary study endpoint will be overall survival. Study treatment will end after a maximum of 3 TACE cycles. Patient survival will be followed from date of first study TACE procedure until a date of death is obtained or the patient is lost to follow-up. Treatments for hepatocellular carcinoma after the study TACE treatments are complete will be documented during the survival period to the extent possible.

For cTACE, 75 mg/m^2 of doxorubicin (maximum dose of 150mg of doxorubicin per TACE cycle) mixed with ethiodized oil will be delivered into the hepatic artery via microcatheter, and then the artery will be occluded with particle PVA. For the hqTACE, the 75 mg/m^2 of doxorubicin (maximum dose of 150mg of doxorubicin per TACE cycle) will be loaded onto the HepaSphere/QuadraSphere Microspheres (through ionic bonding when the spheres are exposed to doxorubicin solubilized in normal saline) and delivered via microcatheter. No ethiodized oil is used with the microspheres. Dosage will be calculated and rounded up to the nearest 25 mg of doxorubicin. The occlusion endpoint will be stasis to the second or third branches. If stasis has not been reached when the target dosage of doxorubicin has been delivered, additional bland embolic (particle PVA for the cTACE arm and HepaSphere/QuadraSphere for the hqTACE arm) will be used to achieve a consistent endpoint.

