9.2.2 Reporting Unanticipated Adverse Events and Serious Adverse Events

Any unanticipated adverse event or SAE, including death, due to any cause that occurs during this investigation, whether or not related to the study treatments, must be reported to the Sponsor immediately (not to exceed 24 hours within site notification of the event) in writing via fax or email. The SAE must be completely described on the AE CRF as well as the provided safety report form.

Safety Contact Information:
Primary Safety Contact: [Redacted] [Redacted] [Redacted] [Redacted]
Medical Monitor [Redacted] [Redacted] [Redacted] [Redacted]

10 Tumor Response Assessment

Response will be assessed using mRECIST criteria to evaluate tumor necrosis, and includes assessment of viable tumor, which is defined as uptake of contrast agent in the arterial phase of MRI.

Central Reviewers will evaluate all liver MRIs for tumor response. Two specially trained interventional radiologists will read each blinded liver MRI. In the event that the reviewers do not agree, a third reader will evaluate the imaging, and this will be the official reading for that

evaluation. Determination of whether a patient receives a third TACE cycle will be based on the results of the central readings, and not the individual clinical sites.

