4.1 Sequence of MRI Scans

According to the study protocol, each patient will undergo up to 3 chemoembolization treatments in both arms. MRI will be performed at baseline and at 3 timepoints post-baseline, according to the following schedule:

MRI examination #1: Baseline (Timepoint 0)
Within 1 month of the first TACE cycle(week -4 to week 0)

MRI examination #2: Timepoint 1
4 weeks after the first TACE cycle (± 1 week)

MRI examination #3: Timepoint 2
4 weeks after the second TACE cycle (± 1 week)

MRI examination #4: Timepoint 3
4 weeks after the third TACE cycle (± 1 weeks)

The protocol requires the second TACE cycle to be performed in all patients 8 weeks (\pm 2 weeks) after the initial TACE cycle, unless the investigator deems further treatment unsafe for the patient, and regardless of the response assessment performed by the independent readers. In contrast, the third TACE cycle will only be done for patients with MRI results after the second TACE cycle that demonstrate less than complete response (CR), as interpreted by the central reviewers according to modified RECIST criteria.

Therefore, the study requires that the central imaging review site provides the investigator site with the response assessment recorded for a given subject after the third MRI examination (the second post-baseline MRI examination).

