[figure not shown]

Figure 1. Synopsis of image data flow and adjudication strategy.

Information regarding the response classification of a given subject after the second TACE cycle (either after the agreement of both primary readers or following adjudication) will be forwarded to a sponsor data manager, who will forward the information to the investigator at the site since this information will determine eligibility for the third TACE cycle in case of less than overall CR.

Overall objective response will be calculated by the sum of complete responses and partial responses recorded at the last available assessment.

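### Stopping for toxicity is written as withdrawal from the study plus a consent request for survival contacts, while stopping for curative therapy keeps survival follow-up by default

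*Combined protocol and SAP*

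**What the plan says.** The Withdrawal of Patients section gives the investigator the right to withdraw a patient from the study for listed reasons. The first is adverse events, with an ejection fraction below 50% named. Withdrawn patients are encouraged to complete the final-visit evaluations if they can, and are asked to consent to survival contacts. This applies at any cycle.

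Two other reasons for stopping TACE early are handled differently:

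- **Complete necrosis after cycle 2 (Section 7.5).** There is no third cycle. "The patient will proceed to Post Final Study TACE evaluations defined in section 7.8".
- **Suitability for transplant, resection or ablation (the Treatment and Assessment text before Section 7.1).** The patient leaves only the treatment part of the study, and survival follow-up continues under the protocol.

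On the cycles themselves, Section 7.4 says: "A second TACE cycle is required for all patients, unless the investigator deems further treatment unsafe for the patient". Section 7.6 says: "A third TACE cycle will be done for patients with MRI results for the liver after the second TACE cycle", provided the central reading shows less than complete necrosis. It does not repeat the safety exception, and neither does the third-cycle footnote to the Schedule of Procedures in Appendix A. Section 5 sets a maximum: "Patients will receive up to 3 TACE cycles".

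The primary analysis is overall survival in all randomized patients (Sections 11.3.2 and 11.5.1). Patients lost to follow-up are censored when last known alive.

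**The concern.** Overall survival needs vital status for every randomized patient, whatever the reason treatment stopped. The plan secures this by default for patients who stop because they did well. For patients who stop because of harm, the written investigator route is to leave the study, and survival contact then depends on the patient's answer to a separate request. If some decline and their status is not found another way, their censoring is tied to toxicity, and toxicity may depend on the arm.

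The protocol itself gives reason to expect a difference between arms. In its background section, the 30-patient randomized trial of the same device reported 20 grade 3 or 4 adverse events with conventional TACE, against 4 (all grade 3) with the microspheres. These are counts of events and not of treatment stops, so they show that a difference is plausible but not how large it would be.

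The missing exception for cycle 3 is a related but separate matter of patient safety. After cycle 2 every patient has laboratory tests and an ejection fraction measurement (Section 7.5), yet Section 7.6 gives those results no role.

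**Working it through.** **1. The routes side by side**

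| Reason TACE stops | Place | What the patient leaves | Survival follow-up |
|---|---|---|---|
| Complete necrosis after cycle 2 | 7.5 | Nothing; no third cycle | Section 7.8 visit, then 7.9 |
| Suitable for curative therapy | Treatment and Assessment | Treatment part only | By default, stated |
| Unsafe before cycle 2 | 7.4 | Cycle 2 not given | Not stated |
| Adverse event that permanently ends study treatment | 9.1.1 | Study treatment | Not stated; the text is a duty to record |
| Adverse event, including ejection fraction below 50% | Withdrawal of Patients | The study | Consent to contacts is requested |

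Only the last row makes survival contact depend on a new answer from the patient. Rows 3 and 4 show that treatment-only safety stops are foreseen but have no stated follow-up path.

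**2. The plan's own figures**

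Inputs: medians of 16 and 24 months, hazard ratio 1.5, two-sided 5%, 85% power, 196 per group (Section 11.2); 218 deaths (Section 11.5.1).

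- Schoenfeld: 4 × (1.960 + 1.036)² / (ln 1.5)² = 218.4, or 219 rounded up. With 218 deaths, power is 84.9%.
- Freedman gives 225 deaths. The mean 24-month death probability under exponential survival is (0.646 + 0.500)/2 = 0.573, and 225/(2 × 0.573) = 196 per group.

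The stated figures are reproduced.

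**3. What one lost patient costs**

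The post-cycle 2 tests serve as the illustration, because all patients have an ejection fraction test then.

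- Unilobar: cycle 2 at week 8 (6–10), tests 4 (3–5) weeks later, so week 12 (9–15).
- Bilobar: second lobe at week 4 (3–5); cycle 2 lobes at weeks 12 (9–15) and 16 (12–20); tests at week 20 (15–25).

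Assume exponential survival, S(t) = 0.5^(t/median). The chance that a patient alive at t dies by month 24 is 1 − S(24)/S(t), with S(24) = 0.354 for cTACE and 0.500 for hqTACE.

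| Time | S(t), cTACE / hqTACE | Death by month 24, cTACE / hqTACE |
|---|---|---|
| Week 12 (2.76 months) | 0.887 / 0.923 | 0.60 / 0.46 |
| Week 20 (4.60 months) | 0.819 / 0.876 | 0.57 / 0.43 |

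Over the full windows (weeks 9 to 25) the ranges are 0.55–0.61 and 0.41–0.47. Each patient lost at this point therefore leaves about half a death unseen.

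**4. Whether power is the issue**

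The documents give no rate of safety withdrawals or refusals. For illustration only, let a share w leave at 5 months with later deaths unseen, and give every patient 24 months of follow-up. Deaths = n × Σ over arms of [(1 − w) × P(death by 24) + w × P(death by 5)], with P(death by 5) = 0.195 and 0.134.

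| w | Deaths, 196 per group (power) | Deaths, 255 per group |
|---|---|---|
| 0 | 224.7 (86.0%) | 292.3 |
| 10% | 208.7 (83.4%) | 271.5 |
| 20% | 192.7 (80.3%) | 250.7 |
| 30% | 176.7 (76.9%) | 229.8 |

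At the planned enrolment of 255 per group, even w = 30% leaves more than 218 deaths. The exposure is therefore to informative censoring more than to lost power.

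**The case against.** The strongest reply is that the plan already follows these patients. Section 7.8 applies to anyone who has had a final TACE cycle, and Section 7.9 follows patients from first embolization until death or loss to follow-up. Withdrawal is a right of the investigator and not a duty, so a site could stop TACE and keep the patient in the study. The consent request is itself an effort to retain the patient. Nothing says that refusal ends ascertainment, and Section 7.9 allows status from medical records or family. The consent form is not among the documents, so what the entry consent covers cannot be seen.

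All of this stands, and it limits the point. It does not remove it. The general sections permit a treatment-only safety stop without saying so, while the section that names toxicity points to study withdrawal.

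A reader might also infer that the plan compels an unsafe third cycle, or that the central readers overrule the treating physician on safety. The documents do not support either.

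- Section 10 says "whether a patient receives a third TACE cycle will be based on the results of the central readings, and not the individual clinical sites", but it does so directly after the two-reader rules; it settles whose MRI reading counts.
- Charter Section 4.1 requires cycle 2 "unless the investigator deems further treatment unsafe for the patient, and regardless of the response assessment performed by the independent readers" and continues "In contrast, the third TACE cycle will only be done for patients with MRI results after the second TACE cycle" showing less than complete response. The contrast is that cycle 2 ignores response and cycle 3 depends on it.
- Charter Section 4.2 speaks only of eligibility: "since this information will determine eligibility for the third TACE cycle in case of less than overall CR".
- Three cycles is a maximum, and the protocol compliance section allows deviation for an immediate hazard.

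Finally, adding the safety exception to cycle 3 would do nothing for survival ascertainment, and the consent step is not specific to cycle 3. The two changes need separate reasons.

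**Conclusion.** The point holds as a gap in how safety stops are handled at any cycle. Followed as written, the withdrawal route for toxicity can produce treatment-related censoring of the primary endpoint, whereas stopping for curative therapy does not carry that step. This should be corrected.

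The size cannot be estimated. About half a death per lost patient before month 24 rests on the design medians, exponential survival, average prognosis and loss at the post-cycle 2 tests. Any loss at that time would cost the same, so the figure shows what is at stake per patient and is not evidence of harm. Patients stopped for toxicity may not have average prognosis, and the analysis may come before month 24 for some patients if 218 deaths occur first.

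A reader might infer a known bias toward one arm. The documents do not show that: there is no rate of safety stops, no rate of refusal, and no information on the prognosis of those who would refuse. The absent exception in Section 7.6 is a smaller matter of consistency and patient safety.

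**What to change.** **Main change, Withdrawal of Patients section.** State that when TACE is stopped for safety at any cycle, including for an ejection fraction below 50%, the patient leaves only the treatment part of the study, completes the Section 7.8 visit if possible, and remains in survival follow-up under Section 7.9 unless the patient withdraws consent to that follow-up. This extends to safety stops the rule already written for curative therapy.

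**Secondary change, for patient safety.** Add the investigator safety exception from Section 7.4 to the cycle 3 rule in Section 7.6 and to the third-cycle footnote in Appendix A. Section 10 and Charter Section 4.1 can stay as they are, since they concern the MRI reading.

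**Cost.** Wording in three places and a few more 3-monthly survival contacts. There are no added procedures and no change to sample size, endpoints or imaging.
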